## 6 BIOMARKER ANALYSIS

Biomarker analyses will be subject to a separate analysis plan and report, with the exception of HPV status that will be presented in the summary of baseline characteristics and as a subgroup factor for efficacy analyses.

## 7 IMMUNOGENICITY ANALYSIS

Immunogenicity analyses will be subject to a separate analysis plan and report.

QMD Ref: Worldwide-TMP-ST-054-1.0_Effective: 12Aug2022	Governing QMD: Worldwide-SOP-ST-026
Confidentiality Statement	

This document is the property of Worldwide Clinical Trials Inc. and may not be duplicated, copied, altered or removed from company without prior approval from Worldwide Quality Assurance or in compliance with Worldwide Standard Operating Procedures.

Worldwide Clinical Trials Controlled Quality Management Document		
 WORLDWIDE CLINICAL TRIALS	Sponsor:	Flamingo Therapeutics
	Protocol Number:	FLM-6774-201
STATISTICAL ANALYSIS PLAN		

## 8 INTERIM ANALYSIS

An interim futility analysis is planned for when ORR can be assessed for the first 39 patients. Tumor assessment data for the interim analysis will be restricted to up until the earliest date in which all 39 patients have received at least one dose of study drug. All demographic and safety data reported until the time of the datacut will be included in the report.

The final ORR analysis is planned after 81 patients are followed for a minimum of 3 months (2 radiologic scans). A 2:1 combination: control randomization will be used for the 2 arms and the (Futility stopping) stop enrolling patients and claim that the experimental arm is unacceptable if:

$$Pr(ORR_{comb} > ORR_{con} | data) < \lambda(n/N)\alpha,$$

Where  $\lambda=0.96$  and  $\alpha=0.94$  are design parameters optimized to maximize the power under  $H0$ :  $ORR_{con} = 0.15$  and  $ORR_{comb} = 0.43$ , while controlling the type I error rate at 0.05 under  $ORR_{con} = ORR_{comb} = 0.15$ . This optimization is performed assuming a vague prior Beta(0.5,0.5) for  $ORR_{con}$  and  $ORR_{comb}$ .

Based on the above decision rule, to reject the null hypothesis and conclude that the combination arm is superior compared to the control:

At the interim analysis:  $Pr(ORR_{comb} > ORR_{con} | data) > 0.5$ , and

At the final analysis:  $Pr(ORR_{comb} > ORR_{con} | data) > 0.96$

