3 STUDY DESIGN

3.1 Overall Study Design

This is a multicenter, open-label, Phase II, randomized, controlled study to determine the efficacy, safety, and other indicators of clinical and biological activity of the combination of danvatirsen and pembrolizumab as first-line treatment for R/M HNSCC.

After providing informed consent, patients will be assessed for eligibility during the screening phase of the study. All patients must be willing and able to provide a formalin-fixed paraffin-embedded (FFPE) archival or fresh tumor sample collected during the screening period; a fresh biopsy is preferred if safe and feasible to obtain and consented to by the patient. Following the screening period, eligible patients will be randomized in a 2:1 ratio to danvatirsen + pembrolizumab or pembrolizumab monotherapy, respectively.

Patients will be stratified by CPS (CPS ≥ 1 and < 20 vs. CPS ≥ 20). An early assessment of response in patients with CPS ≥ 1 and < 20 will be performed and should the response rate in this subgroup not pass the minimum desired efficacy level, eligibility will be restricted to patients with CPS ≥ 20 .

Patients will receive treatment in 21-day cycles. Patients assigned to the pembrolizumab monotherapy arm will receive treatment until a criterion for discontinuation is met or a maximum of 24 months/34 cycles of treatment. Patients assigned to combination therapy will receive both treatments until a criterion for discontinuation is met or the patient has received a maximum of 24 months/34 cycles of pembrolizumab, after which they may remain on danvatirsen monotherapy.

As the combination of danvatirsen and pembrolizumab has not been evaluated previously, safety will be assessed on a continuous basis. A formal review of safety will be performed by the Safety Review Committee after the first 9 patients randomized have completed at least one cycle of the assigned study treatment. If accrual reaches 20 patients prior to availability of the safety results, accrual will be suspended. If the combination is deemed intolerable, further accrual will be halted.

[figure not shown]
A futility analysis will be conducted when ORR can be assessed for the first 39 patients, as described in more detail in [Section 9.2](#).

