Patients in both treatment arms will have radiologic tumor assessments every 6 weeks (± 1 week), regardless of treatment delays, until objective disease progression, initiation of new anticancer treatment, death, withdrawal of consent, or end of study, whichever occurs first.

All patients who discontinue study treatment for any reason will have a safety follow-up visit 30 days (+7 days) after the last dose of study treatment and a follow-up for AEs 90 days (+7 days) after the last dose of pembrolizumab. Patients will be followed for survival at 12-week (± 7 days) intervals until death or withdrawal of consent, whichever occurs first. Survival follow-up will continue until at least 15 months after the last patient is randomized in the study.

The study design is depicted in [Figure 1](#).

Figure 1: Study Scheme

Note: Maximum duration of pembrolizumab treatment is 24 months; there is no limit to the duration of danvatirsen treatment.

Abbreviations: PD = progressive disease; Q3W = every 3 weeks; QW = weekly; SFU = safety follow-up & survival follow-up

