7.7 Imaging Assessments

For all patients, tumor response assessment will be obtained by radiographic imaging with contrast-enhanced CT (preferred) or MRI evaluation. Optimal anatomic coverage for most solid tumors include the chest, abdomen, and pelvis. Coverage should encompass all areas of known predilection for metastases in the disease under evaluation and should additionally investigate areas that may be involved based on signs and symptoms of individual patients. In general, lesions present at baseline should be followed using the same imaging methodology and imaging equipment at subsequent assessments.

Tumor response assessments will be based on evaluation of response of target, non-target, and new lesions according to RECIST v1.1, as detailed in [Appendix 5](#) (all measurements should be recorded in metric notation). Following initial objective response (PR or CR per RECIST v1.1), confirmatory imaging studies should be obtained 4 to 6 weeks later ([Eisenhauer et al 2009](#)).

Before stopping treatment, confirmation of PD should be considered by imaging no less than 4 weeks after initial progression.

The timing of on-study imaging should follow calendar days and **should not** be adjusted for delays in treatment administration or for visits. The same imaging technique should be used in a patient throughout the study for consistency.

For patients who discontinue study treatment for reasons other than PD, radiographic scans should continue according to the respective schedule of assessment until PD, initiation of new anticancer therapy, withdrawal of consent, or at least 15 months after the last patient is

randomized in the study, whichever comes first. Additional imaging may be performed if clinically indicated per the Investigator's discretion.

Brain MRI with or without contrast is the preferred brain imaging modality; however, CT is acceptable if MRI is clinically contraindicated. Patients with treated or untreated parenchymal brain metastases, leptomeningeal disease, or current active malignant epidural disease are excluded from participation in the study (see [Section 4.2](#)). Patients with previously treated epidural disease are allowed as long as disease is inactive. Patients are not required to have brain imaging at screening unless there are suggestive clinical symptoms/suspicion.

During the study, brain CT/MRI scans should be conducted if clinically indicated by development of new specific symptoms.

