9.2 Sample Size

Sample size considerations were based on monitoring the primary efficacy endpoint, ORR, using a 2-arm Bayesian optimal phase 2 (BOP2) design (Zhao et al 2022).

Specifically, let n denote the interim sample size and N denote the maximum sample size. Let ORR_{con} denote the control ORR and ORR_{comb} denote the combination treatment ORR. We define the null hypothesis $H_0: ORR_{comb} \leq ORR_{con}$, under which the combination arm is deemed as unacceptable, respective to the control. We employ the following Bayesian rule to make a go/no-go decision:

(Futility stopping) stop enrolling patients and claim that the experimental arm is unacceptable if:

$$Pr(ORR_{comb} > ORR_{con} | data) < \lambda \left(\frac{n}{N}\right)^\alpha,$$

Where $\lambda=0.96$ and $\alpha=0.94$ are design parameters optimized to maximize the power under $H_0: ORR_{con} = 0.15$ and $ORR_{comb} = 0.43$, while controlling the type I error rate at 0.05 under $ORR_{con} = ORR_{comb} = 0.15$. This optimization is performed assuming a vague prior Beta(0.5,0.5) for ORR_{con} and ORR_{comb} .

An interim futility analysis is planned when ORR can be assessed for the first 39 patients, and the final ORR analysis is planned after 81 patients are followed for a minimum of 3 months (2 radiologic scans). A 2:1 combination:control randomization will be used for the 2 arms and will yield 83% power at the 1-sided 5% alpha based on the above decision rule to reject the null hypothesis and conclude that the combination arm is superior compared to the control:

At the interim analysis: $Pr(ORR_{comb} > ORR_{con} | data) > 0.5$, and

At the final analysis: $Pr(ORR_{comb} > ORR_{con} | data) > 0.96$

The go/no-go criteria, also presented in detail in Table 9 below, are non-binding.

The operating characteristics of the design, based on 100000 simulations using the BOP2 application, are presented in Table 10.

Table 9: Optimized Stopping Boundaries

Control N	Combination N	# CR/PR in Control	Stop for Futility if # of CR/PR in Combination - # of CR/PR in Control ≤
13	26	0	0
13	26	1~2	1
13	26	3	2
13	26	4	3
13	26	5	4
13	26	6	5
13	26	7	6
13	26	8	7
13	26	9	8
13	26	10	9
13	26	11	10
13	26	12	11
13	26	13	12
27	54	0	4
27	54	1	7
27	54	2	10
27	54	3	11
27	54	4	13
27	54	5	15
27	54	6	16
27	54	7	17
27	54	8	18
27	54	9	20
27	54	10	21
27	54	11	22
27	54	12~13	23
27	54	14	24
27	54	15	25
27	54	16~17	26
27	54	18~19	27
27	54	20~26	28
27	54	27	27

Abbreviations: CR = complete response; PR = partial response

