Table 10: Operating Characteristics

Scenario	% ORR Control	% ORR Combination	Early Futility Stopping (%)	Claim Promising (%)	Average Sample Size
1	15	15	46.1	4.6	62
2	23	23	43.8	4.5	63
3	20	40	7.1	54.6	78
4	23	43	7.7	52.9	78
5	25	50	4.5	68.6	79
6	15	43	1.9	82.7	80

Abbreviation: ORR = objective response rate

Additional futility monitoring criteria will be taken into consideration for the subgroup of patients with CPS ≥ 1 and < 20 . Specifically, if no more than one patient achieves a response (confirmed or unconfirmed CR or PR within the first two scans) in the first 10 patients enrolled in the combination arm for this subgroup, there will be no further enrollment in this subgroup, and the study will continue to enroll in the CPS ≥ 20 subgroup, consistent with any guidance based on the monitoring criteria outlined in [Table 9](#). Additionally, accrual in the CPS ≥ 1 and < 20 subgroup will pause, if no responses have been achieved, but response data for the first 10 patients in that subgroup are not yet mature, defined as at least 2 scans assessed.

Considering the limited size of the CPS ≥ 1 and < 20 subgroup, the futility criteria were derived based on a single arm BOP2 design with the interim assessment after 10 patients, a final assessment of 27 patients (half of the intended size of the combination arm) testing a null hypothesis of 15% ORR (KEYNOTE-048 pembrolizumab monotherapy ORR for this subgroup ([Burtness et al 2022](#))) vs. an alternative hypothesis of 29% ORR (SCORES combination arm for this subgroup), at 1-sided 10% level with approximately 65% power.

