## 5.12 Efficacy Analyses

All efficacy analyses will be presented by planned treatment for the FAS.

All statistical tests will be performed using a two-tailed 5% overall significance level, unless otherwise stated. All comparisons between treatments will be reported with 90% and 95% confidence intervals for the difference.

The following efficacy parameters will be derived as per RECIST v1.1 for the FAS.

- Overall Response Rate
- Disease Control Rate
- Complete Response Rate
- Duration of Response
- Progression-Free Survival
- Overall Survival

A summary of RECIST v1.1 tumor assessments, methods, and criteria are presented in Appendix 5 of the protocol. All efficacy parameters are derived from overall response as per RECIST v1.1. Overall response at each tumor assessment is determined using measurements of both target and non-target lesions. The overall response categories are as follows.

All target lesion, non-target lesion, and new lesion data will be listed separately.

Overall Response Categories by RECIST v.1.1	
CR	Complete Response
PR	Partial Response
SD	Stable Disease
PD	Progressive Disease
NE	Not Evaluable

A response of CR or PR must be confirmed by a repeat assessment at least 4 weeks after the initial CR or PR. A tumor assessment at least 35 days after the first dose is required for an overall response of SD, otherwise the BOR is considered not evaluable (NE).

Overall response rate (ORR), complete response rate (CR), and disease control rate (DCR) are each calculated using the subject's best overall response (BOR) on study. This is determined based on the following hierarchy for overall response category:

CR > PR > SD > PD > NE

Tumor assessments after the first PD will not be considered for BOR.

QMD Ref: Worldwide-TMP-ST-054-1.0_Effective: 12Aug2022	Governing QMD: Worldwide-SOP-ST-026
Confidentiality Statement	

This document is the property of Worldwide Clinical Trials Inc. and may not be duplicated, copied, altered or removed from company without prior approval from Worldwide Quality Assurance or in compliance with Worldwide Standard Operating Procedures.

Worldwide Clinical Trials Controlled Quality Management Document			
 WORLDWIDE CLINICAL TRIALS	Sponsor:	Flamingo Therapeutics	
	Protocol Number:	FLM-6774-201	
STATISTICAL ANALYSIS PLAN			

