### 5.12.2 Primary Efficacy Analysis

The primary efficacy analysis for ORR will be conducted once all patients are treated and followed for a minimum of 3 months (2 radiologic scans).

The number and percentage of patients with each BOR category will be summarized.

The ORR will be defined as the proportion of patients with a confirmed objective response as assessed by the Investigator in the FAS. “Patients who receive at least one dose of either study

QMD Ref: Worldwide-TMP-ST-054-1.0_Effective: 12Aug2022	Governing QMD: Worldwide-SOP-ST-026
Confidentiality Statement	

This document is the property of Worldwide Clinical Trials Inc. and may not be duplicated, copied, altered or removed from company without prior approval from Worldwide Quality Assurance or in compliance with Worldwide Standard Operating Procedures.

Worldwide Clinical Trials Controlled Quality Management Document			
 WORLDWIDE CLINICAL TRIALS	Sponsor:	Flamingo Therapeutics	
	Protocol Number:	FLM-6774-201	
STATISTICAL ANALYSIS PLAN			

treatment but have no valid post-baseline tumor assessment or not available confirmed BOR will be considered non-responders.”

The ORR estimate along with the corresponding 2-sided 90% and 95% confidence interval using Clopper-Pearson exact binomial test will be presented for each treatment arm.

Comparison of the ORR between treatment arms will be analyzed using Fisher’s Exact test and by reporting the risk difference and corresponding 90% and 95% confidence intervals. Both a 1-tailed and 2-tailed p-value for Fisher’s Exact test will be provided. The risk difference for ORR is calculated as the difference in ORR between both treatment arms. Confidence intervals for the risk difference will be calculated using the Wald Method.

The following SAS code will be used, where adrs\_freq is a frequency table of planned treatment by responder status. (Sorted so that first row is responders for the combination arm).

ORR Estimate and Corresponding Exact Binomial Confidence Intervals:

```
ods output binomial=<outdata>;
proc freq data=adrs_freq;
  tables avalc / binomial(level="RESPONDER") alpha=0.05;
  by trt01pn;
  weight count;
run;
Lower Limit is nvalue1 where name1="XL_BIN".
Upper Limit is nvalue1 where name1="XU_BIN".
Use alpha=0.10 for 90% CI.
```

Risk Difference and Corresponding Confidence Intervals:

```
ods output riskdiffcol2=<outdata>;
proc freq data=adrs_freq order=data;
  tables trt01pn*avalc / riskdiff alpha=0.05;
  weight count;
run;

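### SAP Section 8 cuts interim tumour data on the day the 39th patient is first dosed, so the futility boundaries would be read before response is known

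*SAP*

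**What the plan says.** **When the interim happens.** Protocol 9.2: "An interim futility analysis is planned when ORR can be assessed for the first 39 patients". Protocol 3.1 and the first sentence of SAP 8 set the same trigger.

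**Which tumour data it uses.** The next sentence of SAP 8 has tumour data "restricted to up until the earliest date in which all 39 patients have received at least one dose of study drug".

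**How response is measured.** Protocol 3.1: "Patients in both treatment arms will have radiologic tumor assessments every 6 weeks" (with a window of 1 week either side). After a first CR or PR, Protocol 7.7 says "confirmatory imaging studies should be obtained 4 to 6 weeks later". SAP 5.12 adds: "A response of CR or PR must be confirmed by a repeat assessment at least 4 weeks after the initial CR or PR". Under SAP 5.12.2, patients who have had study "treatment but have no valid post-baseline tumor assessment or not available confirmed BOR will be considered non-responders".

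**Standards used elsewhere.** SAP 8 requires at least 3 months (2 scans) for the final ORR. The separate futility look in the CPS 1 to <20 subgroup (Protocol 9.2) treats data as mature after 2 scans and counts "confirmed or unconfirmed CR or PR within the first two scans". Table 9 labels its counts only as CR/PR.

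**Status.** Protocol 9.2 and 9.10.2 make the futility criteria non-binding. SAP 9 says the final analysis comes early because the study was terminated. It does not say whether the interim was run.

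**The concern.** The trigger and the data cut cannot both be followed. On the day the last of the 39 is first dosed, that patient has no post-baseline scan. Patients dosed in the preceding 6 weeks or so have none either, and those dosed in the preceding 10 to 12 weeks cannot have a confirmed response. No other section reconciles the two sentences.

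SAP 8 gives no scoring rule for the interim. The natural inference from SAP 5.1 and 5.12.2 is that every dosed patient is in the denominator and anyone without a confirmed response is a non-responder. The interim rows of Table 9 (13 control, 26 combination) assume that all 39 outcomes are known. Hidden responses shrink the visible difference between arms while the boundaries stay put; with no visible response in either arm, Table 9 says stop. What is at stake is mainly false futility advice for a combination that works.

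A single trial can also be misread the other way, because control responses are hidden too. Mature counts of 3 control and 5 combination (difference 2, boundary 2) stop. Seen as 1 and 4 (difference 3, boundary 1), they continue.

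**Working it through.** **1. Reproduce the plan's figures.** Inputs from Protocol 9.2: Beta(0.5, 0.5) priors, λ = 0.96, α = 0.94, looks at 13/26 and 27/54. The cut-off is 0.96 × (39/81)^0.94 = 0.483 at the interim and 0.96 at the end. These regenerate every row of Table 9. Exact binomial enumeration over both looks then gives:

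| Control / combination ORR | Early stop: Table 10 | Exact | Claim promising: Table 10 | Exact |
|---|---|---|---|---|
| 15 / 43 | 1.9% | 1.93% | 82.7% | 82.56% |
| 20 / 40 | 7.1% | 7.14% | 54.6% | 54.4% |
| 15 / 15 | 46.1% | 46.4% | 4.6% | 4.53% |
| 23 / 23 | 43.8% | 44.1% | 4.5% | 4.4% |

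The printed properties therefore assume mature interim data.

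**2. Who lacks data at the SAP cut.** The documents give no accrual rate. Assume the 39 accrue evenly over A weeks, with A from 78 down to 26. The number followed for less than t weeks is 39 × t/A.

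- No scan (t = 6): 39 × 6/78 = 3, up to 39 × 6/26 = 9.
- No confirmed response possible (t = 10 to 12): 39 × 10/78 = 5, up to 39 × 12/26 = 18.

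**3. Chance that an eventual response is visible.** Let w be the share of responders first seen at a given scan (weeks 6, 12, 18) and t the week the response counts. Then q = Σ w(1 − t/A), taken as equal in both arms. Response timing is also assumed: 50/30/20% at scans 1/2/3, or all at scan 1. Example, A = 26 with confirmation after 4 weeks: q = 0.5(1 − 10/26) + 0.3(1 − 16/26) + 0.2(1 − 22/26) = 0.45. Expected counts at 15% versus 43% fall from 1.95 and 11.18 (13 × 0.15; 26 × 0.43) to about 0.9 and 5.1.

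**4. Results at 15% versus 43%.** Mature responses are thinned by q at the interim, final data are mature, and the rule is followed. Cells show q; early stop; power.

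| Scoring and timing | A = 26 | A = 39 | A = 52 | A = 78 |
|---|---|---|---|---|
| Confirmed after 4 weeks, 50/30/20 | 0.45; 10.9%; 76.3% | 0.64; 5.8%; 80.3% | 0.73; 4.4%; 81.2% | 0.82; 3.3%; 81.9% |
| Confirmed after 6 weeks, 50/30/20 | 0.38; 14.7%; 73.3% | 0.58; 6.8%; 79.5% | 0.69; 4.9%; 80.9% | 0.79; 3.6%; 81.7% |
| All at scan 1, confirmed week 12 | 0.54; 8.0%; 78.6% | 0.69; 4.8%; 80.9% | 0.77; 3.8%; 81.6% | 0.85; 3.1%; 82.0% |
| All at scan 1, confirmed week 10 | 0.62; 6.1%; 80.0% | 0.74; 4.1%; 81.4% | 0.81; 3.4%; 81.8% | 0.87; 2.8%; 82.1% |
| Unconfirmed, 50/30/20 | 0.61; 6.3%; 79.9% | 0.74; 4.2%; 81.3% | 0.80; 3.5%; 81.8% | 0.87; 2.9%; 82.1% |
| Unconfirmed, all at scan 1 | 0.77; 3.8%; 81.6% | 0.85; 3.1%; 82.0% | 0.88; 2.7%; 82.2% | 0.92; 2.4%; 82.3% |

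**5. Other scenarios, same range of q.**

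- 20% versus 40%: early stop 8.8% to 23.1% confirmed and 8.1% to 13.6% unconfirmed, against 7.1% printed.
- 15% versus 15%, confirmed: early stop 48.1% to 56.1%, against 46.4% mature. Between 4.4% and 10.9% of trials flip from a mature stop to continue, and 6.0% to 20.5% flip the other way.
- 15% versus 15%, final claim rate: 3.6% to 4.5%, against 4.5% mature.

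**6. With a 2-scan cut.** Follow-up is then uniform on 12 to 12 + A weeks. Under confirmed scoring with 50/30/20 timing, q = 0.84 to 0.96. Early stop at 15% versus 43% is 2.2% to 3.1%, about 7.7% to 9.3% at 20% versus 40%, and power at 15% versus 43% is about 82.0% to 82.5%. If all responses appear at scan 1, early stop returns to 1.9%.

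**The case against.** - **The rule is advice only.** Non-binding criteria let the sponsor see that data are immature and carry on, and type I error does not rise. This stands, and it limits the consequence. It does not make the two sentences compatible.
- **The large figures rest on assumed accrual and timing.** Also true. The 14.7% needs 26-week accrual, late responses and 6-week confirmation. At 52 to 78 weeks, confirmed scoring gives 2.8% to 4.9% early stopping and power of at least 80.9%. Any accrual pause before the 39th patient would move results towards that mild end. Every case still exceeds 1.9%.
- **Interim scoring is not stated.** This is why both scorings are shown. SAP 11 points to confirmed scoring: it marks the main ORR table for the interim and leaves the confirmed-or-unconfirmed sensitivity table unmarked.
- **The study has already ended early.** If the interim was run, new wording cannot change it; if it was never reached, the sentence was never used. This is the strongest point, and it puts disclosure ahead of rewording.
- **A 2-scan cut is not full maturity.** Correct: a response first seen at week 12 or later may still await confirmation. Patients lost to follow-up do not hold up the cut, since Protocol 6.3 treats them as withdrawn.

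**Conclusion.** The concern holds. SAP 8 contradicts its own trigger and Protocol 3.1 and 9.2, and applying its cut as written means reading Table 9 on incomplete counts. That part rests on the text alone.

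The size depends on assumed even, uninterrupted accrual and assumed response timing. Over the range examined, early stopping at 15% versus 43% is 2.8% to 14.7% confirmed, or 2.4% to 6.3% unconfirmed, instead of 1.9%. Power, if the rule is followed, is between about 82% and 73.3%. The damage is false futility and unreliable advice in both directions, not a higher false-positive rate. Nothing in the documents shows that this interim was run or that it led to the termination, so no actual harm is claimed.

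**What to change.** **First, disclose.** If the interim was run under the first-dose cut, report the cut date and the number per arm with fewer than 2 scans on that date, and repeat the Table 9 reading on mature data.

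**Then replace the cut-off sentence in SAP 8**, for example with:

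> Interim tumour data are cut on the date by which every one of the first 39 patients has at least 3 months of follow-up (2 post-baseline scans) or has earlier had PD, died, started new anticancer therapy or withdrawn. Response is scored under Section 5.12.2.

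This is the standard SAP 8 already applies to the final ORR. Responses still awaiting confirmation should be shown per arm beside the confirmed count; counting them would bring early stopping at 15% versus 43% to 2.0% to 2.2%.

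**Cost.** Two SAP sentences and no protocol amendment, plus the repeat calculation if an interim took place. The cut falls about 12 to 13 weeks after the SAP's date, a delay the protocol trigger already implies. No enrolment pause is stated for this look. At 39/78 = 0.5 to 39/26 = 1.5 patients a week, about 6 to 20 more would therefore be enrolled by then (45 to 59 of 81), which reduces the saving from an early stop.

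### Protocol 9.2 and SAP 8 require an interim probability above 0.5 before H0 can be rejected, which conflicts with the futility rule's non-binding status and with Table 9

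*SAP*

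**What the plan says.** Protocol 9.2 sets a two-arm BOP2 design with one futility look, with sample sizes counted in patients: "An interim futility analysis is planned when ORR can be assessed for the first 39 patients, and the final ORR analysis is planned after 81". The stop applies when the posterior probability that the combination ORR exceeds the control ORR falls below a cut-off given by a formula. Table 9 turns that cut-off into response counts.

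Both documents then state a two-part route to rejecting H0: interim probability above 0.5, and final probability above 0.96. In the protocol this list completes the power sentence ("A 2:1 combination:control randomization will be used for the 2 arms and will yield 83% power at the 1-sided 5% alpha"). In SAP 8 the power clause is gone and the list stands as a decision rule: "Based on the above decision rule, to reject the null hypothesis and conclude that the combination arm is superior compared to the control".

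The status of the interim rule differs between the documents:
- Protocol 9.2, straight after the two-part list: "The go/no-go criteria, also presented in detail in Table 9 below, are non-binding". Protocol 9.10.2 and the synopsis repeat the non-binding status.
- SAP 8 keeps the instruction to "stop enrolling patients and claim that the experimental arm is unacceptable if" the probability is below the cut-off. It does not say that the rule is non-binding, nor does any other section of the SAP.
- SAP 9, which lists changes from the protocol, mentions only the early termination.

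**The concern.** A non-binding futility rule lets the sponsor continue after a crossing and still test at the end. If rejection also needs the interim condition, that final test cannot succeed, however strong the final data. The non-binding status and the two-part rule then give different conclusions for the same data, and the choice between them could be made after the data are known.

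The printed 0.5 adds a second problem. It is stricter than the formula and Table 9, so a sponsor who follows Table 9 exactly could continue correctly and still be barred from a superiority claim.

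**Working it through.** **Inputs**, all from Protocol 9.2: 13 control and 26 combination patients at the interim, 27 and 54 at the final; Beta(0.5, 0.5) prior in each arm; lambda 0.96, exponent 0.94; ORR pairs from Table 10.

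**Cut-off.** Interim: 0.96 × (39/81)^0.94 = 0.96 × 0.503 = 0.483. Final: n = N, so 0.96.

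**Method.** For x responders among n patients the posterior is Beta(0.5 + x, 0.5 + n − x). The probability that the combination ORR is higher was found by numerical integration for every pair of counts. Exact binomial probabilities were then summed over all interim and final outcomes.

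**Reproducing the plan.** With 0.483 and 0.96, every boundary in Table 9 is recovered. Against Table 10:
- 15% v 43%: success 82.6% (plan 82.7%), early stop 1.9% (plan 1.9%), average N 80.2 (plan 80).
- 15% v 15%: success 4.5% (plan 4.6%), early stop 46.4% (plan 46.1%), average N 61.5 (plan 62).

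Two things follow. Table 10 assumes the stop is always obeyed: 81 − 0.461 × 42 = 61.6, its average N of 62. It also rests on 0.483, because a cut-off of 0.5 would stop 54.8% of trials under the null, not 46.1%.

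**Where 0.5 and Table 9 disagree.** Five interim outcomes lie between the two cut-offs. As control/combination responders they are 2/4, 3/6, 4/8, 5/10 and 6/12, with probabilities 0.484, 0.490, 0.493, 0.496 and 0.499. Table 9 says continue; the rejection rule says fail. They occur in 3.45 − 1.93 = 1.5% of trials at 15% v 43%, and in 54.78 − 46.44 = 8.3% at 15% v 15%.

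**Success denied.** In each cell the first figure uses 0.483 and the second uses 0.5. All are percentages of trials. Denied means the interim condition fails but the final probability exceeds 0.96. Differences were taken before rounding.

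| Control v combination | Interim condition fails | Success, interim enforced | Success, final rule alone | Denied |
|---|---|---|---|---|
| 15 v 43 | 1.93 / 3.45 | 82.56 / 82.15 | 82.80 | 0.24 / 0.65 |
| 20 v 40 | 7.14 / 11.10 | 54.38 / 53.92 | 54.68 | 0.30 / 0.76 |
| 23 v 43 | 7.79 / 11.79 | 52.82 / 52.35 | 53.15 | 0.33 / 0.79 |
| 25 v 50 | 4.52 / 6.90 | 68.40 / 67.94 | 68.77 | 0.37 / 0.83 |
| 15 v 15 | 46.44 / 54.78 | 4.53 / 4.51 | 4.61 | 0.08 / 0.09 |
| 23 v 23 | 44.10 / 54.34 | 4.39 / 4.33 | 4.44 | 0.04 / 0.11 |

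At 15% v 43%, 12.6% of trials that cross at 0.483 would still reach a final probability above 0.96: 1.93 × 0.126 = 0.24 points. The five disputed outcomes add 0.65 − 0.24 = 0.41 points, and that part arises with no override at all.

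**Type I error without the interim condition.** It is 4.61% at the design null of 15%. Over common null rates it peaks at about 5.3% near an ORR of 10%, against about 5.2% with the stop enforced at the Table 9 boundary.

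**The case against.** A reader might infer that the SAP alone turned a non-binding rule into a binding one. The documents do not support that. Protocol 9.2 has the same stop wording and the same two-part rule, so the tension starts there. The SAP's own fault is the missing sentence. SAP 1 also bases its analyses on Protocol Amendment 4, which does call the rule non-binding, so silence in SAP 8 is an omission and not an express contradiction.

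A reader might also infer that no trial continued past the interim could be declared positive. That is too broad. At 15% v 43%, 96.5% of trials have interim probability above 0.5 and can still succeed. The bar applies only at 0.5 or below, and only to the BOP2 rule. Fisher's exact test in SAP 5.12.2 carries no interim condition, and Protocol 9.10.2 allows advancement on a lower ORR in view of the CR rate.

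A third inference would be that the final rule keeps type I error below 5% at every null rate. It does not near an ORR of 10%, but neither does the enforced rule, and the plan claims control only at 15%.

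It can also be said that 0.5 is just 0.483 rounded, that the loss is under one percentage point, and that SAP 9 announces a final analysis before the Section 8 conditions are met. Rounding is plausible, though the documents do not say so, and it changes the decision at five outcomes. The small size and the early termination both stand and limit the practical effect. SAP 9 does not, however, replace the success rule in SAP 8, so the rule still needs one clear meaning.

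**Conclusion.** The point holds as an inconsistency in the decision rule that starts in Protocol 9.2 and is carried into SAP 8 without the qualifying sentence. Read literally, a trial that continues with interim probability of 0.5 or less cannot be declared superior by the BOP2 rule, even where Table 9 told it to continue. Success is denied in 0.24 to 0.65 points of trials at 15% v 43%, and in 0.33 to 0.79 points at 23% v 43%.

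These figures assume looks at exactly 13/26 and 27/54. The upper figures assume continuation to 81 patients after every interim value of 0.5 or less; the lower ones, after every crossing at 0.483. The stated 5% alpha at 15% and the 83% power do not depend on the interim condition. The reason to correct the text is that the decision rule should be unambiguous; the gain in power is minor.

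**What to change.** In SAP 8:
- State that the interim futility criterion is non-binding, as the protocol does.
- Replace the interim 0.5 with 0.483, and refer to Table 9 for the counts.
- State that at the final analysis H0 is rejected if the posterior probability exceeds 0.96, whatever the interim result.
- Quote the operating characteristics of that rule: type I error 4.6% at the design null of 15% (about 5.3% near a common ORR of 10%, against 5.2% with the interim enforced) and power 82.8% at 15% v 43%. Note that Table 10 assumes the stop is obeyed.

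Clarify Protocol 9.2 in the same way, or record the change in SAP 9, so that the two rejection rules do not diverge. The cost is a few sentences. It needs no new data and no change in sample size, and type I error at the design null moves from 4.5% to 4.6%, still within the stated 5%.
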